9.5.3. Immunogenicity Analysis

The analyses of immunogenicity will be based on the PP set. If the number of participants in the FAS and PP set differs (defined as the difference divided by the total number of participants in the PP set) by more than 10%, supportive analyses of immunogenicity may be conducted using the FAS.

For the immunogenicity endpoints, the geometric mean of specific antibody titers with corresponding 95% CI at each time point and the geometric mean fold rise (GMFR) of specific antibody titers with the corresponding 95% CI at each post-baseline time point over pre-injection baseline at Day 1 will be provided by treatment arm, with adjustment for baseline antibody titer and other potential covariates, including age group and primary vaccine type. Descriptive summary statistics, including median, minimum, and maximum, will also be provided.

For summarizations of geometric mean titer, antibody titers reported as below the lower limit of quantification (LLOQ) will be replaced by $0.5 \times LLOQ$. Values that are greater than the upper limit of quantification (ULOQ) will be converted to the ULOQ.

For mRNA-1010, seroconversion rate from baseline will be provided with a 2-sided 95% CI using the Clopper-Pearson method at each post-baseline time point. Rate of seroconversion is defined as the proportion of participants with either a pre-vaccination HAI titer < 1:10 and a post-vaccination HAI titer $\ge 1:40$ or a pre-vaccination HAI titer $\ge 1:10$ and a minimum 4-fold rise in post-vaccination HAI antibody titer.

For mRNA-1273, seroresponse is defined as either: participants with GMFR in nAb or bAb titers of \geq 4-fold at Day 29 compared to Day 1 in those with baseline titer \geq LLOQ, or Day 29 titer \geq 4 × LLOQ if baseline titer is < LLOQ.

The immunogenicity of mRNA-1073 will follow the same rules as mRNA-1010 and mRNA-1273.

Between-group comparisons will be evaluated in terms of immunogenicity endpoints (GMR and SCR/SRR difference) in the PP set and will be specified in the SAP in greater detail.

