5.3. Lifestyle Restrictions

Participants must not eat or drink anything hot or cold within 10 minutes before oral temperature is taken. Participants in the study should defer vaccination with an approved COVID-19 vaccine

mRNA-1073

or seasonal influenza vaccine until after completion of their Day 29 visit, and ideally until Day 181 visit, if such vaccines are available, and they have discussed with the investigators and have chosen to receive it.

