The use of the following concomitant medications and/or vaccines will not require withdrawal of the participant from the study but may determine a participant's evaluability in the per-protocol (PP) analysis (analysis sets are described in Section 9.4):

- Any investigational or nonregistered product (drug or vaccine) other than the IPs used during the study period.
- Immunosuppressants or other immune-modifying drugs administered chronically (ie, more than 14 days in total) during the study period. For corticosteroids, this will mean that prednisone ≥ 10 mg/day or the equivalent is not permitted. Inhaled, nasal, and topical steroids are allowed.
- Long-acting immune-modifying drugs administered at any time during the study period (eg, infliximab).
- An authorized or licensed vaccine administered during the period from 28 days before through 28 days after vaccination.
- Immunoglobulins and/or any blood products administered during the study period.
- Antiviral and antiretroviral medications.

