9.4. Analysis Sets

The analysis sets are described in Table 8.

Table 8 Analysis Sets

Set	Description	
Randomization Set	The randomization set consists of all participants who are randomly assigned.	
FAS ¹	The FAS consists of all randomly assigned participants who receive the IP.	
PP Set ²	The PP set consists of all participants in the FAS who comply with the injection schedule, comply with the timings of immunogenicity blood sampling to have a baseline and at least 1 post-injection assessment, do not have influenza or SARS-CoV-2 infection at baseline and post-baseline up to Day 29 (as documented by positive RT-PCR testing result), and have no major protocol deviations and/or prohibited concomitant medication use (documented in the Section 6.5.3) that are prespecified with impacts on the immune response and should be excluded from the PP set.	
Safety Set ³	The safety set consists of all randomly assigned participants who receive the IP.	

Set	Description	
Solicited Safety Set ⁴	The solicited safety set consists of all participants in the safety set who contribute any solicited AR data.	

Abbreviations: AR = adverse reaction; FAS = full analysis set; IP = investigational product; PP = per-protocol.

- ¹ For the FAS, participants will be analyzed according to the group to which they were randomized.
- ² The PP set will be used as the primary analysis set for analyses of immunogenicity unless otherwise specified. Participants will be analyzed according to the group to which they were randomized.
- ³ The safety set will be used for all analyses of safety, except for the solicited ARs. Participants will be included in the vaccination group corresponding to what they actually received.
- ⁴ The solicited safety set will be used for the analyses of solicited ARs and participants will be included in the vaccination group corresponding to what they actually received.

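### The Day 181 titers are analysed in a per-protocol set that stops screening for infection and licensed vaccines at about Day 29, so they can include responses to later vaccination or infection

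*Protocol*

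**What the plan says.** Section 9.5.3 states: "The analyses of immunogenicity will be based on the PP set". It asks for GMTs at each time point, GMFRs "with the corresponding 95% CI at each post-baseline time point over pre-injection baseline at Day 1", and seroconversion at each post-baseline time point. Between-group GMRs and rate differences also use the PP set. Seroresponse is defined in Section 9.5.3 at Day 29 only, but the second secondary objective in Table 2 (Section 3) carries both response rates to all evaluable humoral time points. Section 4.1 and Table 1 place the humoral samples at Days 1, 8, 29 and 181.

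Three passages determine which Day 181 titers are kept:

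- **Infection.** Table 8 in Section 9.4 keeps participants who "do not have influenza or SARS-CoV-2 infection at baseline and post-baseline up to Day 29", as documented by RT-PCR.
- **Licensed vaccines.** Section 6.5.3 lists, among exposures that may affect PP evaluability: "An authorized or licensed vaccine administered during the period from 28 days before through 28 days after vaccination".
- **Permitted vaccination.** Section 5.3 asks participants to defer an approved COVID-19 "or seasonal influenza vaccine until after completion of their Day 29 visit, and ideally until Day 181 visit".

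Other items in Section 6.5.3 run longer. One is "Any investigational or nonregistered product (drug or vaccine) other than the IPs used during the study period". Another, "Antiviral and antiretroviral medications", carries no time limit.

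**The concern.** Day 181 is the only humoral sample after Day 29, so it is the only late evidence for the second secondary objective. The screening window suits Day 29 but is applied unchanged to a sample drawn about five months later. A licensed influenza or COVID-19 vaccine on, say, Day 60 can directly raise the titer being measured, and so can an infection. Under the stated rule that titer still counts as a response to the study vaccine, even when the event has been recorded correctly.

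What is at stake is the reading of Day 181 GMT, GMFR, seroconversion, seroresponse and any between-group comparison at that visit. Group 1 receives no study influenza antigen and Group 2 no study SARS-CoV-2 antigen. Either could show a Day 181 rise to an antigen it never received in the trial.

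**Working it through.** The protocol states no figure on this point, so there is none to reproduce. Table 7 concerns the chance of seeing an adverse event and does not bear on titers.

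**Length of the unscreened period.** Day 29 to Day 181 is 181 − 29 = 152 days of the 180 after injection, and 152/180 = 84%. With the ±14-day window in Table 1 it is 138 to 166 days.

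**Calendar.** The Synopsis estimates first enrolment in May 2022 and last completion in December 2022. Day 1 on 1 May gives a Day 181 window of 14 October to 11 November. Day 1 on 30 June gives a window opening on 13 December. Exclusion criterion 11 means nobody had an influenza vaccine in the 180 days before randomization. Later vaccination is plausible, but the protocol gives no rate.

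**Level within an arm.** Let a share f of an arm be vaccinated or infected after Day 29, with the Day 181 titer multiplied by k. The mean log titer rises by f·log k, so GMT and GMFR are multiplied by k^f. Both inputs are assumptions.

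| f | k = 2 | k = 4 | k = 8 |
|---|---|---|---|
| 0.1 | 1.07 | 1.15 | 1.23 |
| 0.2 | 1.15 | 1.32 | 1.52 |
| 0.3 | 1.23 | 1.52 | 1.87 |
| 0.5 | 1.41 | 2.00 | 2.83 |

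For scale, assume a log10 SD of 0.4 to 0.6. The 95% CI of one arm's GMT at n = 100 is then a factor of 10^(1.96 × SD/10) either way, or 1.20 to 1.31. A 4-fold boost in 20% of the arm (1.32) is already slightly larger.

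**Response rate.** If a share p would respond from study vaccine alone and a share q of boosted participants respond, the observed rate is p(1 − f) + q·f. With assumed p = 0.2, q = 0.7 and f = 0.3 this is 0.14 + 0.21 = 0.35.

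**Ratio between arms.** Two cases must be kept apart.

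- *Proportional boost, same f and k in both arms.* The ratio is (k^f × A)/(k^f × B) = A/B, so the GMR is unchanged.
- *Boosted participants reach the same titer in both arms, same f.* The log difference is multiplied by 1 − f, so the GMR becomes GMR^(1−f). A true 2.0 reads 1.87, 1.62 and 1.41 at f = 0.1, 0.3 and 0.5. A true 0.67 reads 0.76 at f = 0.3 and 0.82 at f = 0.5.

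**The case against.** The strongest reply is that this belongs in the SAP, which is not at hand. Table 8 defines which participants belong to the PP set and does not say that every sample from them is used. The objective speaks of *evaluable* time points, and the PP set is primary unless otherwise specified. A Day 29 cut-off is also sensible for membership, because removing people for later events would discard valid Day 29 titers. The last point stands and shapes the fix. The rest does not fully answer the concern. The protocol fixes the cut-off itself and applies that set to every time point. *Evaluable* is left undefined. The introduction to Section 9 says that changes to methods for secondary objectives after study start call for a protocol amendment. The possible FAS analysis in Section 9.5.3 would not remove these titers either.

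The second reply is that little hangs on it. The study is descriptive (Section 9.2), the first secondary objective is at Day 29, and the interim analysis uses data only up to Day 29. No passage ties a decision to Day 181 titers specifically. This stands and limits the severity.

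Third, including or censoring such titers is a choice of estimand, and censoring after infection conditions on a post-randomization event that may depend on the vaccine response. This also stands, so results under other handling are needed alongside.

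A reader might infer three stronger things that the documents do not support:

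- *All later non-study vaccination goes unscreened.* Investigational vaccines are covered for the whole study period, and the untimed antiviral item may remove some treated infections at discretion.
- *Any boost common to all arms pulls GMRs toward 1.* The proportional case above leaves them unchanged.
- *Group 2 will be infected more often, so the other arms will look less lasting.* Every participant has completed a COVID-19 primary series (inclusion criterion 7), and a difference in infection is conjecture.

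**Conclusion.** The concern holds in a limited form. Day 181 titers in the PP set can include responses to licensed vaccines or to infection after Day 29. Whether they do, and by how much, depends on uptake and infection rates that the protocol does not give. Under the assumed 4-fold boost, GMT and GMFR inflation is 1.15-fold with 10% of an arm affected and 1.52-fold with 30%. Seroconversion and seroresponse can rise too. Shrinkage of the GMR toward 1 rests on the further assumption that boosted participants reach a similar titer in all arms.

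Day 29 results and the interim analysis are untouched, and no alpha or power is involved. The matter should be fixed before Day 181 data are interpreted. It is not a defect that undermines the study.

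**What to change.** Keep PP membership as it is for Day 29. Add to Sections 9.4 and 9.5.3, and to the Synopsis, a sample-level rule for samples after Day 29:

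- exclude an influenza titer drawn after a non-study influenza vaccine or RT-PCR-confirmed influenza;
- exclude a SARS-CoV-2 titer drawn after a non-study COVID-19 vaccine or RT-PCR-confirmed SARS-CoV-2 infection.

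Report the numbers excluded by arm and reason. Show two sensitivity analyses of Day 181: one without censoring, and one censoring for vaccination only.

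The cost is a few sentences and the extra tables. No new data are needed: Section 6.5.2 records non-study vaccinations through Day 181, and Section 8.1.8 provides weekly symptom reporting with RT-PCR on swabs over the same period. The change affects analysis only. There will be fewer Day 181 titers, censoring for infection conditions on a post-randomization event, and undetected asymptomatic infections will remain. The report should state these limits.

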For the immunogenicity endpoints, the geometric mean of specific antibody titers with corresponding 95% CI at each time point and the geometric mean fold rise (GMFR) of specific antibody titers with the corresponding 95% CI at each post-baseline time point over preinjection baseline at Day 1 will be provided by treatment arm, with adjustment for baseline antibody titer and other potential covariates, including age group and primary vaccine type. Descriptive summary statistics, including median, minimum, and maximum, will also be provided.

For summarizations of geometric mean titer, antibody titers reported as below the lower limit of quantification (LLOQ) will be replaced by $0.5 \times LLOQ$. Values that are greater than the upper limit of quantification (ULOQ) will be converted to the ULOQ.

For mRNA-1010, seroconversion rate from baseline will be provided with a 2-sided 95% CI using the Clopper-Pearson method at each post-baseline time point. Rate of seroconversion is defined as the proportion of participants with either a pre-vaccination HAI titer < 1:10 and a post-vaccination HAI titer $\ge 1:40$ or a pre-vaccination HAI titer $\ge 1:10$ and a minimum 4-fold rise in post-vaccination HAI antibody titer.

For mRNA-1273, seroresponse is defined as either: participants with GMFR in nAb or (binding antibody) bAb titers of \geq 4-fold at Day 29 compared to Day 1 in those with baseline titer \geq LLOQ, or Day 29 titer \geq 4 × LLOQ if baseline titer is \leq LLOQ.

The immunogenicity of mRNA-1073 will follow the same rules as mRNA-1010 and mRNA-1273.

Planned Analyses:

An interim analysis (IA) and a final analysis will be conducted in the study.

The IA will be performed after all the 550 participants randomized into Group 1 through Group 6 have completed their Day 29 visit assessments and will include the safety and immunogenicity data collected up to Day 29. Either nAb or bAb assay will be used for assessment of immunogenicity. The IA will be performed by a separate team of unblinded programmers and statisticians. The analysis will be presented by vaccination groups. Except for a limited number of Sponsor and CRO personnel who will be unblinded to perform the IA, the study site staff, investigators, study monitors, and participants will remain blinded until after the final database lock for final analysis.

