9.2. Statistical Hypotheses

No formal hypotheses will be tested. All analyses will be descriptive and presented by vaccine group.

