9.3. Sample Size Determination

The sample size for this study is not driven by statistical assumptions for formal hypothesis testing. The number of proposed participants is considered sufficient to provide a descriptive summary of the safety and immunogenicity of different study groups.

The study will enroll approximately 550 generally healthy adults 18 to 75 years of age who were previously fully vaccinated for COVID-19 primary series with a locally authorized and approved SARS-CoV-2 vaccine, and their last COVID-19 vaccine must be \geq 120 days prior to the randomization visit (or less per local guidance). Participants must not have received a licensed influenza vaccine within \leq 180 days of randomization and have not had known history of confirmed influenza infection within \leq 180 days or SARS-CoV-2 infection within \leq 90 days of Screening. The number of participants and groups are shown in Table 3.

Approximately 550 participants will be enrolled at a CCI Asample size of 100 participants in one group has at least an 85% (or 95%) probability to observe at least 1 participant with an AE at a true 2% (or 3%) AE rate (Table 7).

Table 7 Randomized Sample Size Calculations

Sample Size	True AE Rate	Probability to Observe 0 AEs	Power to Detect at Least 1 AE
50	0.05	7.7%	92.3%
50	0.03	21.8%	78.2%
100	0.03	4.8%	95.2%
100	0.02	13.3%	86.7%

Abbreviation: AE = adverse event.

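### The protocol caps every titer above the ULOQ even if a measured value exists; if many SARS-CoV-2 titers exceed the ULOQ, GMTs and GMRs are distorted and their CIs too narrow

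*Protocol*

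**What the plan says.** In section 9.5.3 the paragraph on titers outside the quantifiable range begins "For summarizations of geometric mean titer, antibody titers reported as below the lower limit of quantification (LLOQ) will be replaced by" half the LLOQ, and goes on: "Values that are greater than the upper limit of quantification (ULOQ) will be converted to the ULOQ". The Synopsis (section 1.1, Immunogenicity Analyses) has the same rule: titers above the limit "will be converted to the ULOQ". Neither place makes an exception for a value the laboratory has quantified above the limit.

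The 4-fold definitions stand in later paragraphs of section 9.5.3. Influenza seroconversion needs a "minimum 4-fold rise in post-vaccination HAI antibody titer" when baseline is at least 1:10. SARS-CoV-2 seroresponse is worded as "participants with GMFR in nAb or bAb titers of" at least 4-fold when baseline is at or above the LLOQ. Neither mentions the ULOQ.

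The section closes with "Between-group comparisons will be evaluated in terms of immunogenicity endpoints (GMR and SCR/SRR difference) in the PP set", leaving further detail to the SAP. Section 9.2 says "No formal hypotheses will be tested. All analyses will be descriptive and presented by vaccine group".

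**The concern.** Inclusion criterion 7 requires a completed COVID-19 primary series and allows a booster. Exclusion criterion 14 rules out known SARS-CoV-2 infection only within 90 days. Five of the six groups in Table 3 (1 and 3 to 6) then receive a further SARS-CoV-2 antigen. High titers at baseline and at Day 29 are therefore plausible. Section 8.2 leaves the SARS-CoV-2 assay open between a pseudovirus neutralization assay and a multiplex binding assay, so a single rule covers assays whose upper limits are not stated.

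Capping discards information in the upper tail. The arm with more titers above the limit loses more, and the spread of log titers shrinks. The Amendment 2 rationale says the sponsor will use safety and immunogenicity data from these participants to choose a dose for Phase 2/3. With no formal test planned, the GMR and its interval are the immunogenicity evidence a reader will use to compare the combined vaccine with co-administration and to compare dose levels.

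**Working it through.** **Inputs from the protocol.** The cap, the GMR and SCR/SRR comparisons and the 4-fold thresholds (section 9.5.3), and 100 participants per group except 50 in Group 1 (Table 3). No stated figure depends on the cap. The only statistical calculation, Table 7, is 1-(1-p)^n for observing at least one adverse event; its four entries reproduce (92.3%, 78.2%, 95.2%, 86.7%) but do not bear on this point.

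**Assumptions, not in the protocol.** Log10 titers are normal; the reference arm has mean 0 and the test arm mean log10(GMR); both share one ULOQ, U, placed so that a chosen share of the reference arm exceeds it. No baseline adjustment is modelled.

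**Step 1: GMR with equal spreads.** The mean of a capped normal is E[min(X,U)] = μΦ(a) - σφ(a) + U(1-Φ(a)), with a = (U-μ)/σ. The apparent GMR is 10^(test mean - reference mean).

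Example with σ = 0.4, true GMR 0.80 and 20% above the ULOQ: U = 0.8416 × 0.4 = 0.3366. Reference mean: -0.4 × 0.2800 + 0.3366 × 0.20 = -0.0447. Test arm: μ = -0.0969, a = 1.084, capped mean -0.1252. Apparent GMR = 10^(-0.0805) = 0.831.

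Over σ = 0.3 to 0.5:

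| Share of reference arm above ULOQ | True 0.80 reads | True 0.67 reads |
|---|---|---|
| 5% | about 0.807 | about 0.68 |
| 10% | 0.814-0.815 | about 0.69 |
| 20% | 0.829-0.832 | 0.71 |
| 40% | 0.863-0.868 | 0.75-0.77 |

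**Step 2: GMR with unequal spreads.** The same formula with a larger SD in the test arm:

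- SD 0.5 against 0.4, 10% of the reference arm above the ULOQ: a true 0.80 reads 0.785 and a true 1.0 reads 0.953.
- SD 0.6 against 0.4: a true 0.80 reads 0.761, 0.747 and 0.733 at 5%, 10% and 20%.

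These move away from 1. In the 5% case the test arm itself has more above the limit: U = 1.645 × 0.4 = 0.658, and 1-Φ((0.658 + 0.097)/0.6) is about 10%.

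**Step 3: interval width.** With 10%, 20% and 40% above the ULOQ, the reference-arm SD after capping is 0.915, 0.833 and 0.668 of its true value. Assume 85 evaluable per arm, σ = 0.4, 20% above and a true GMR of 0.80. Uncapped, the standard error is 0.4 × √(2/85) = 0.0614 and the unadjusted lower 95% bound is 10^(-0.0969 - 1.96 × 0.0614) = 0.61. Capped, the standard error is 0.0526 and the bound is 10^(-0.0805 - 1.96 × 0.0526) = 0.66.

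**Step 4: seroresponse, if capped titers feed the 4-fold rule.** No recorded Day 29 value can exceed the ULOQ, so a baseline above ULOQ/4 cannot show a 4-fold rise. Simulation with 2,000,000 draws (assumed baseline SD 0.5, fold-rise SD 0.35, log10 scale):

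| Geometric mean fold rise, reference vs test | Reference Day 29 above ULOQ | Baseline above ULOQ/4 | SRR reference / test | Difference |
|---|---|---|---|---|
| 10 vs 7 | 0% | 0% | 87.3% / 75.7% | -11.6 points |
| 10 vs 7 | 10% | 0.9% | 86.5% / 75.0% | -11.5 |
| 10 vs 7 | 20% | 3.4% | 84.3% / 73.1% | -11.2 |
| 6 vs 4 | 0% | 0% | 69.3% / 50.0% | -19.3 |
| 6 vs 4 | 10% | 2.8% | 67.4% / 48.7% | -18.7 |
| 6 vs 4 | 20% | 8.4% | 63.5% / 45.8% | -17.7 |

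The rate falls in both arms and the difference shrinks by at most 1.6 points.

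**The case against.** Setting values above the ULOQ to the ULOQ is a usual convention. Sensitivity models and tables of the share above the limit normally belong in the SAP, which is not shown, so their absence from the protocol is no fault. That stands. What remains is the replacement rule itself, which the protocol fixes without exception.

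The size cannot be determined from this document. With no titers above the ULOQ nothing happens, and no passage says that the laboratory reports values above the limit. With 100 per arm and SD 0.3 to 0.5, the unadjusted 95% interval for a GMR is roughly the estimate multiplied or divided by 1.21 to 1.38, so a shift from 0.80 to 0.815 lies well within it. This also stands, and limits the point to the case of an appreciable share above the limit.

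A reader might infer that the rule favours a finding of no interference. The documents do not support that. The pull toward 1 depends on similar spreads and can reverse (step 2). Section 9.2 plans no hypothesis test, section 9.3 says "The sample size for this study is not driven by statistical assumptions for formal hypothesis testing", and no margin or no-interference criterion exists. A reader might also infer that participants with high baselines can never be seroresponders. That needs the cap to carry over from the paragraph on geometric mean titers to the later definitions, which the text does not say; even then it holds only above ULOQ/4 and affects all randomized arms.

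**Conclusion.** The point holds conditionally. The cap is current, appears twice and would overwrite any quantified value above the ULOQ. If an appreciable share of SARS-CoV-2 titers exceeds the limit, GMTs and GMRs are distorted and their intervals are too narrow for the quantities they are meant to estimate. With similar spreads the shift in a true GMR of 0.80 is about 0.015 at 10%, 0.03 at 20% and 0.06 to 0.07 at 40%, toward 1; at 5% or less it is under 0.01. With clearly unequal spreads the direction can reverse, and the shift need not be small even at 5% of the reference arm. Any effect on seroresponse would mainly lower the absolute rates.

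All sizes rest on assumed log-normal titers, spreads and shares above the limit, without the planned baseline adjustment. This is a worthwhile improvement to a descriptive analysis that informs dose selection. It does not show that a comparison is biased in a known direction.

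**What to change.** In section 9.5.3 and the Synopsis, amend the sentence to: *Values greater than the ULOQ will be converted to the ULOQ only if no actual value is available.* This requires no new re-dilution of samples; where the laboratory reports nothing above the limit, the primary analysis is unchanged.

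Where more than 5% of titers in any arm at a visit exceed the ULOQ, add a sensitivity GMT and GMR from a censored-normal (Tobit) model on log titers with the same covariates. Because the trigger applies to any arm, it also catches the unequal-spread example in which 5% of the reference arm but about 10% of the test arm lie above the limit.

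The cost is one sentence and one conditional model, best settled before the Day 29 interim analysis (section 9.6.1). The small downside is that the sensitivity analysis relies on log-normality.
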